and VA CLCs. Case-mix adjusted regional and facility variation in the rate of re-hospitalization among PAC Medicare SNF patients has been shown to relate to states' policies, facility resources and medical staff engagement.[7] VHA CLCs have medical and administrative staff that are under central control and therefore, at least theoretically, have the same organizational incentives as does the hospital director. These aligned incentives could mean that efforts to reduce re-hospitalizations in the VHA should be successful.

One systematic review of interventions to reduce hospitalizations from NHs classified interventions into those that increased staffing, altered provider incentives, identified high risk patients and introduced changes into the system of care.[22] Although changing the financial incentives could decrease avoidable transfers, it can also result in inadequate care if the infrastructure to manage residents with acute changes doesn't exist. Disseminating and implementing interventions that can assist NH staff manage acute changes in resident clinical status are critical to reducing avoidable hospitalizations of NH residents.

Interventions to Reduce Acute Care Transfers (INTERACT) is a quality improvement program involving a set of evidence-based clinical practice tools and strategies initially developed under a Centers for Medicare & Medicaid Services (CMS) contract to Georgia's Medicare Quality Improvement Organization. The original INTERACT tools were developed with input from a panel of expert NH clinicians and pilot tested in three Georgia NHs with high hospitalization rates. More recently, INTERACT II was evaluated in 25 NHs in three states in a 6-month quality improvement initiative that provided tools, on-site education, and teleconferences every 2 weeks by an experienced nurse practitioner. There was a 17% reduction in hospital admissions in these 25 NHs from the same 6-month period in the previous year. The group of 17 NHs rated as engaged in the initiative had a 24% reduction, compared with 6% in the group of eight NHs rated as not engaged and 3% in a comparison group of 11 NHs. The average cost of the 6-month implementation was \$7,700 per NH while the projected savings to Medicare in a 100-bed NH were approximately \$125,000 per year.[11]

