Based upon merged VIREC and Medicare inpatient and outpatient data and CLC nurse staffing and other organizational data, we will match CLCs in terms of hospitalization rate, proximity to their VAMC hospital, admissions per bed and the mix of short and long stay CLC Veterans they serve. Up to 15 pairs of CLCs will be identified and from each pair one CLC will be randomly selected and approached about implementing the INTERACT program. We expect a minimum of 8 of the facilities approached to accept, adopt and implement the program over the 6 month training period and the additional 24 month implementation and data collection period (encompassing: a 12 month monitoring and data collection period to review the results of the intervention, followed by 12 months of indirect data monitoring). Both members of the CLC matched pairs will be dropped from the study if the CLC that is randomly selected to be offered the INTERACT program declines to participate. During the 6 month training period and the 12 month active monitoring and data collection period, extensive process measures, such as CLC staff participation in online training and support conference calls, will be gathered for use in both the implementation analyses as well as the Budget Impact Analysis (BIA). Additionally, quality improvement tools applied by staff to examine the characteristics and “avoidability” of hospitalizations during the 6 month training and 12 month active monitoring period will be assembled and coded. There will be no contact with pair matched control CLC since outcome data on their hospitalization rates will come exclusively from existing data. Changes in the case-mix composition and seasonally adjusted hospitalization rates for both the intervention and control CLC in each pair will be examined by comparing data from the two years prior to the introduction of INTERACT with data from the two years after the introduction of INTERACT.

Data Sources: To estimate the impact of the INTERACT on the rate of hospitalization from CLCs a variety of administrative data will be used. Our strategy for merging data is described below.

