Once CLCs are matched, the randomly selected CLC will be approached to solicit their participation with the strong endorsement of GEC leadership. We will approach the randomly selected experimental CLCs until up to 15 have agreed. If a CLC declines to participate, both members of the pair of matched CLCs will be dropped from consideration. The matched “control” case of those CLCs that agree to participate in the INTERACT program will not be approached. The “control” status of a CLC will be known to no one outside of the project research team and will not be divulged in any project description or publication.

Patient Selection: We do not anticipate excluding any Veterans in CLCs from the population to be included in the outcome analyses. The CLC is the unit of random assignment, meaning the intervention changes the skills of CLC staff. For each CLC agreeing to adopt the INTERACT program, it will be as if the CLC is introducing a focused quality improvement program to their staff. As such, no individual patient consent will be requested. We will separately examine hospitalization rates of Veterans classified as long stay or short stay based upon the pattern of recent admission and discharge data, but this will be regardless of their clinical condition or diagnoses.

Outcome Measures: The primary outcome (on which our statistical power estimates were based) will be the **overall hospitalization rate** calculated as the number of admissions to hospital from

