CLC agreement to participate: Up to 15 CLCs will be identified as potential participants in the INTERACT intervention program based on a pair matching system and random selection of one CLC from each pair. If the selected CLC does not agree to participate the pair will be dropped and we will go back to the remaining list of potential pair matches and select another site until up to 15 have agreed to participate or we have contacted all eligible sites.

The formal training at each CLC is scheduled to occur over a 6 month period followed by 12-18 additional months of observation. A minimum level of participation in the training is required to

ascertain that the intervention has been embraced by the CLC staff. The Providence research staff will monitor the CLCs' participation in the intervention. If a CLC is doing poorly and the Champions seem to be unable to engage and motivate the staff, we may drop the site or try to recruit an additional Champion(s). This is one of the reasons for matching extra pairs of CLCs. One of the strengths of the pair matched design is that if one of the intervention CLCs is dropped we can readily drop the matched control site without having to worry about unbalancing the design.

Each CLC will follow the procedure below to become an active participating CLC in the INTERACT intervention. Selected CLCs will be contacted with a letter from the PI, [name], Co-PI [name], MPH, INTERACT Developer, [name], and GEC leadership containing introductory material, describing the INTERACT training program being proposed. After the letter, follow up contact will be made with each CLC to determine participation. Sites who agree to participate will be asked to sign a Research Study Agreement (See Appendix # 3, Research Study Agreement).

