We will test the effect of INTERACT on the rate of hospitalization from CLCs taking advantage of *both* the paired control CLCs as well as the differences in the hospitalization rates among intervention facilities before and after the implementation of the intervention. The primary outcome variable is the monthly rate of hospitalization, which, after adjusting for seasonality and trends in the rate over several years prior to the intervention, is compared to the rate of the paired comparison CLC. To allow for regional differences in seasonality, separate ARIMA models will be run for each CLC and then we will use the monthly difference between the observed to the expected CLC hospitalization rate value to compare between the two matched CLCs, aggregating these differences overall pairs. Technically, the average monthly rate of hospitalization before the intervention will be compared to the average monthly rate after and the difference between these two rates will be compared to the differences in the rates of the comparison facilities, using a standard *difference in difference* design.

A similar approach will be used with the person level, risk adjusted hospitalization rates for short and long stay residents calibrated as an annualized rate and there will be fewer facility years than were facility months under the approach described above. The unit of analysis will be the CLC resident but the standard errors will be clustered at the facility level.

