Aim #5: *To conduct a Budget Impact Analysis (BIA) of the INTERACT program from a VA perspective, using the 2-year study follow-up period as the time horizon. Given the important public policy implications for Medicare, we will conduct a secondary BIA from the perspective of the entire Federal Government. The purpose of the BIA is to provide VA managers with the budget impact information they need to manage the start-up and implementation of the program if this project demonstrates that INTERACT works in VA. Preliminary non-VA studies have found INTERACT to save more than 15 times the cost of the intervention. Thus, even if INTERACT is less effective in VA, it still should yield significant savings.*

The BIA will be driven by the other Aims' estimates of the VA effectiveness of INTERACT. As part of the intervention, we will carefully track both the start-up and on-going labor associated with INTERACT. Actual VA labor costs will be used to value this time. The cost savings of the program are not directly observed as they are the hospitalizations that INTERACT prevents, and thus must be estimated. We will obtain data on all VA and Medicare hospitalizations and other types of care. VA costs will be obtained from the DSS fee-basis files, and the Medicare reimbursement will be used as the estimated costs of non-VA care. The first analysis will be to compare the hospitalization costs between the intervention and control sites, including looking for offset effects for other types of care (reduced hospitalizations being partially offset by higher costs for other types of care, including higher costs in the CLC).

We will conduct a full sensitivity analysis of the estimated savings, of how quickly they accrue, and of potential off-setting cost increases. The extent of the savings will be driven by how the intervention affects both the rate of hospitalization, and of the types of hospitalizations (costs vary significantly by the types of conditions treated). Another concern is that the DSS cost estimates include fully allocated overhead costs. The details in the DSS cost data will be used to provide information about how the potential cost savings are distributed across variable direct care costs (e.g., supplies and nursing labor), costs that can only be changed over time (e.g., reallocation of space to other types of care), and allocated overhead costs that will not change with the program.

Statistical Considerations:

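### A poorly engaged intervention CLC can be dropped after randomisation together with its control, with no stated threshold or time limit and no rule keeping the pair in the primary analysis; if used, this is likely to inflate the effect

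*Combined protocol and SAP*

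**What the plan says.** The overview of study procedures and the section on CLC selection, matching and random assignment have one CLC per matched pair chosen at random and then approached. Refusals are covered there: "If a CLC declines to participate, both members of the pair of matched CLCs will be dropped from consideration".

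Aim #2B (CLC agreement to participate) adds a second exit, after agreement. It says that "A minimum level of participation in the training is required to" establish that staff have taken the programme up, and gives no level. Research staff monitor participation. For a CLC that does poorly, if "the Champions seem to be unable to engage and motivate the staff, we may drop the site or try to recruit an additional Champion(s". Pairs beyond the number needed were matched partly for this purpose. The control's removal is presented as a strength of the design: "if one of the intervention CLCs is dropped we can readily drop the matched control site without having to worry about unbalancing the design".

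The overview says of the controls: "There will be no contact with pair matched control CLC since outcome data on their hospitalization rates will come exclusively from existing data".

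Aim #4 defines the primary comparison as a difference in difference on monthly rates, "aggregating these differences overall pairs". It does not say whether that means all randomised pairs, all agreeing pairs or all remaining pairs. Aim #5 states that the Budget Impact Analysis is driven by the other aims' "estimates of the VA effectiveness of INTERACT".

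**The concern.** Dropping the control with the intervention site keeps the two arms equal in number. It does not keep them comparable. Engagement is seen and acted on only in the intervention arm: the intervention sites that remain have been filtered, and their controls have not. Randomisation within pairs does not protect against this.

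Two consequences should be kept apart. First, the target changes, from the effect in all CLCs that agreed to the effect in those that engaged, which is likely to be larger. Second, even if INTERACT does nothing, the estimate is biased towards benefit if poorly engaged sites are also those whose hospitalisation rates would have done worse anyway. Instability in a CLC could plausibly cause both.

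The decision is also not shielded from outcomes. Under Data Assurances, the Providence research staff, who monitor participation, also track hospitalisations and mortality in both arms.

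The primary estimate feeds the projected savings. The plan also foresees wider adoption across CLCs if the programme works, and wider adoption would include sites that engage poorly. Dropping sites that decline is an earlier one-sided selection of the same kind, made at the point of agreement.

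**Working it through.** **What dropping a control means.** A control receives no training, no calls and no contact, and contributes only existing data. There is no activity to stop, so dropping it can only mean leaving its outcomes out. Exclusion from the analysis is therefore implied, though not stated, and no supplied section says the reverse.

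**Target shift.** Inputs from the Introduction/Background: "The group of 17 NHs rated as engaged in the initiative had a 24% reduction, compared with 6% in the group of eight NHs" (the eight judged non-engaged), and 17% over all 25 homes. As a check on these, the site-weighted mean is (17×24 + 8×6)/25 = 18.2%, against the 17% reported, which is close enough for illustration. The share not engaged is 8/25 = 32%.

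Assume 12 pairs (the plan gives 8 to 15), 8 engaged at 24% and 4 not engaged at 6%, equally weighted:

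| Poorly engaged pairs dropped | Average reduction | Ratio to all kept |
|---|---|---|
| 0 | (8×24 + 4×6)/12 = 18.0% | 1.00 |
| 1 | (8×24 + 3×6)/11 = 19.1% | 1.06 |
| 2 | (8×24 + 2×6)/10 = 20.4% | 1.13 |
| 4 | (8×24)/8 = 24.0% | 1.33 |

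If 1 to 4 of 8 to 15 pairs are poorly engaged and all of those are dropped, the all-kept average ranges from 22.8% (1 of 15) to 15.0% (4 of 8). The result after dropping is 24%, an overstatement of 5% to 60%. Subtracting the 3% change in the cited comparison homes from both sides of the 12-pair case gives (24.0 − 3)/(18.0 − 3) = 1.40.

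**Bias under no effect.** The plan's power of .77 (8 CLCs, 10% reduction) cannot be rebuilt, because the ARMA coefficients, the error SD and the primary alpha are not given. It can be used for scale. With power = Φ(k√n − 1.96), k = (0.739 + 1.960)/√8 = 0.954, which implies an SD of pair differences of 10/0.954 = 10.5 points. I used 10 and 19 points; the upper value is an assumption.

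Suppose engagement has correlation ρ with the intervention site's own untreated change, site and control have equal variance, and the d least engaged of N pairs are dropped. Then

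bias = ρ × (SD/√2) × m,

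where m is the mean of the N − d largest of N standard normal values. It is 0.148 for 1 of 12, 0.186 for 1 of 9, 0.275 for 2 of 12, 0.318 for 2 of 10, 0.509 for 4 of 12 and 0.516 for 5 of 15. Examples: 0.3 × (10/√2) × 0.148 = 0.31 points, and 0.3 × (19/√2) × 0.186 = 0.75 points.

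Error rates come from simulation of a paired t test (40,000 trials per cell, Monte Carlo SE about 0.1 points). They span ρ from 0.3 to 0.5 and both SDs.

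| Dropped | Bias, ρ = 0.3 (points) | Bias, ρ = 0.5 (points) | Two-sided 5% error | One-sided 5% error |
|---|---|---|---|---|
| One pair (of 9 or 12) | 0.31–0.75 | 0.52–1.25 | 5.1–5.5% | 6.1–7.2% |
| Two pairs (of 10 or 12) | 0.58–1.28 | 0.97–2.13 | 5.3–6.4% | 6.9–9.3% |
| A third (4 of 12, 5 of 15) | 1.08–2.08 | 1.80–3.47 | 5.8–8.9% | 8.6–14.3% |

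At ρ = 0 there is no bias, and the simulated error stays at 4.8–5.2%.

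**The case against.** - **A threshold may exist elsewhere.** The Research Study Agreement (Appendix 3) sets out what is expected of sites and is not in the supplied text. The minimum is tied to training, which lasts six months, so the window may not be wholly open. This is fair: the finding is that no level or date appears in the text supplied. A threshold would limit discretion, but it would not say whether a dropped pair is analysed.
- **Dropping is a fallback.** Adding a Champion is the stated alternative, poor candidates can be screened out before matching, and a lost Champion must be replaced. The fidelity analyses also relate adherence to outcome, which presumes that some weak sites stay in. These make heavy dropping less likely and weaken the carry-over of the 32% share. None defines the primary set.
- **The engaged-site effect may be what was meant.** The Impact of Findings paragraph ties the expected 20% reduction to CLCs that fully implement. That is an expectation. Aim #4 tests intervention against matched control CLCs with no such restriction.
- **The sizes are illustrative.** The 12 pairs, the 4 poorly engaged and the correlation are assumptions. The 24% and 6% are before-after figures, and the power simulation weights pairs by precision, not equally. All of this stands. With one or two drops, the two-sided error barely moves.
- **It may be too late to change conduct.** This version is dated June 2017, and the Gantt chart puts training in 4/15–8/15 and support through 8/16. If that schedule held, the decisions are past. The analysis set and the account of dropped pairs can still be fixed.

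**Conclusion.** The concern holds. The plan permits a discretionary exclusion after randomisation, based on behaviour observed in one arm only, and the primary analysis set is undefined in a way that lets the exclusion take effect.

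The direction is upward if poorly engaged sites benefit less, as in the protocol's own cited data, or if engagement tracks a site's untreated change. The size depends on use. For one or two drops among 12 pairs the target shift is a 6% to 13% overstatement, and it is 33% if all four poorly engaged pairs go. The false-positive cost is small with few drops, and reaches 8.9% two-sided or 14.3% one-sided when a third of pairs are dropped. The plan gives no sidedness for the primary test and no expected number of drops. The documents do not show that any pair was dropped, so every figure is conditional on the rule being used.

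The gap concerns the primary comparison and should be closed before outcomes are compared.

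**What to change.** Replace the drop rule in Aim #2B, and define the set in Aim #4, along these lines:

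> A CLC may stop receiving study support. Every pair whose selected CLC signed the Research Study Agreement stays, with its control, in the primary difference-in-difference analysis for the full 24-month post period, using the existing VA and Medicare data.

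Then:

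- Report the engaged-sites-only result as a labelled secondary analysis, with the minimum participation level and its date written down before outcomes are compared. If staff have already seen outcomes by arm, say so.
- List every pair that declined or stopped support, with date and reason.
- Add a sensitivity analysis of all randomised pairs, decliners included, to show how much selection at agreement matters.
- Base the main Budget Impact Analysis on the all-agreeing estimate.

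The cost is wording, one secondary and one sensitivity analysis. Outcomes are administrative, so no new data collection is needed. The headline effect may be smaller, because poorly engaged sites dilute it. The loss of precision is modest because more pairs are kept. In the 12-pair illustration, with a constant SD per pair, effect × √n goes from 24.0 × √8 = 67.9 to 18.0 × √12 = 62.4, a fall of about 8%.

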An alternate version of the outcome is a ***per-person, risk adjusted, probability of hospitalization*** variable which will be calculated and compared across intervention and control CLC pairs. In 2007, 32% of Veteran's were hospitalized at any time during the course of the year, ranging from under 10% per CLC to nearly 50%. However, since each Veteran had a different number of person months of observation, something that varies across CLCs, these individual probabilities will be examined separately for short and long stay patients. For short stay patients, we'll calculate the proportion with a 30 day re-hospitalization, adjusting for patient characteristics on the admission MDS and the originating hospital diagnosis and length of stay. For long stay residents (those who are residents of a CLC for at least 100 days), we will calculate the likelihood of hospitalization over a 6 month period, adjusting for MDS measured clinical and functional characteristics relying upon the MDS assessment closest to the beginning of the 6 month period. Both of these measures have been extensively used in the literature using Medicare fee for service claims and have been used by [name] and his colleagues at Brown in preparing these measures for use in the Commonwealth Scorecard system to rate states' health care system.[2][[37]]

The underlying intent of the intervention is to decrease transfers by avoiding decline, appropriately managing acute change or decline in the CLC, and improving the use of advance care plans. Transfer rates alone do not tell us whether these kinds of changes occurred in association with the focused intention of the intervention, i.e. to reduce the rate of potentially avoidable hospitalizations. We will therefore also examine the overall rates of ***potentially avoidable and inappropriate transfers*** prior to the intervention compared to these rates during the consolidation phase of the intervention (among only the CLCs exposed to the INTERACT program), using a tested and reliable structured implicit review process. The Structured Implicit Review (SIR) yields numerous judgments about the need for transferring the Veteran to the hospital and attributes this decision to whether identifiable clinical care problems had been missed and the expected benefits of hospitalization. The final outcome variable is an ordinal variable ranking the hospitalization in terms of the degree of "avoidability".

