Using the results of the Structured Implicit Review process, we will determine the percent of hospital transfers rated as avoidable through better quality of preventive care and early change recognition and the percent rated as inappropriate because the Veteran’s condition could have been safely managed in an average VA CLC. We will compare the percentage hospitalized before the implementation to that after implementation. The sample size of 326 hospitalization records, 163 pre and 163 post-INTERACT, is based upon the assumption that the pre-intervention rate of potentially avoidable hospitalizations will be 40%. For the overall project, we are hypothesizing that there will be a 20% reduction in hospitalizations. Logically, the reductions in hospitalizations will come primarily from the "avoidable" type (otherwise we have a causal inconsistency). Thus, if 40 of 100 hospitalizations pre INTERACT are avoidable and all of the 20% reduction in hospitalizations (20 of 100) will come from among those that are avoidable, we expect a 50% reduction in the rate of avoidable hospitalizations. So, if the pre rate is 40% and the post rate is 20%, using a one tailed test at the alpha .05 level, we need about 100 records

before and 100 after to achieve a power of .90. In the event that some "unavoidable" hospitalizations are really avoided due to the intervention, we increase the sample size to 163 per time period.

Finally, we will test for unintended consequences by examining changes in the rates of overall mortality and in the rate of decline in the late loss ADLs, as measured by the MDS 3.0 nursing home resident assessment, which is done upon admission, periodically thereafter and upon discharge.[45]

Random selection of records with a transfer: A total of 326 medical records with a transfer to the hospital and across the eight intervention CLC sites will be reviewed, 163 pre-INTERACT intervention and 163 post-intervention.

The 163 pre-INTERACT records will be selected from a list of transfers that occurred during the 18 months prior to INTERACT being introduced to the CLCs. This list will be compiled by the study programmer/analysts who will pull it from current CDW data and MDS data. Once the list is generated, random selection will occur to obtain 163 records pre-intervention.

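### Facility-clustered standard errors with 16 to 30 facilities, no small-sample correction and no stated role for the pairs do not secure the 5% error rate of the resident-level hospitalization analyses

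*Combined protocol and SAP*

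**What the plan says.** Aim #4 has two layers. The first is the primary analysis: "The primary outcome variable is the monthly rate of hospitalization", adjusted for season and trend by a separate time-series model for each CLC, then compared within matched pairs and combined over pairs.

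The second is the resident-level analysis: "A similar approach will be used with the person level, risk adjusted hospitalization rates for short and long stay residents", followed by the one sentence on inference: "The unit of analysis will be the CLC resident but the standard errors will be clustered at the facility level". Outcome Measures gives this outcome's status: "An alternate version of the outcome is a" risk-adjusted probability for each resident, examined separately for short and long stay.

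On the number of clusters, the Study Procedures overview says "Up to 15 pairs of CLCs will be identified and from each pair one CLC will be randomly selected", and also "We expect a minimum of 8 of the facilities approached to accept, adopt and implement the program". The chart-review part of Aim #4 speaks of records "across the eight intervention CLC sites will be reviewed". Aim #2B allows a pair to be dropped later if its intervention site does poorly.

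No section names a variance estimator, a small-sample correction, degrees of freedom, a bootstrap or a randomisation test for the resident-level analysis. Alpha and sidedness are not stated for it either; the only stated alpha, one-tailed .05, belongs to the chart review.

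**The concern.** The cluster-robust variance is justified as the number of clusters grows, not as the number of residents grows. With 16 clusters the plain version is biased downward, and a normal critical value ignores how variable it is. Unequal cluster sizes make both problems worse. Unequal sizes are to be expected here: the matching section sorted 64 CLCs into 10 groups by patient-day pattern, so members of a pair are alike in size but different pairs need not be.

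Randomisation was within pairs, so the evidence on the treatment effect is 8 to 15 within-pair contrasts. A method that does not say what it does with the pairs can give very different error rates depending on a modelling choice that the plan leaves open.

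At stake are the p-values and intervals for the hospitalization results that adjust for individual residents' characteristics.

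**Working it through.** The plan gives no error rate, power or sample size for the resident-level analysis, so there is no figure to reproduce first.

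**Inputs from the documents.** Number of facilities G = 16 (8 pairs) to 30 (15 pairs); the CLC is the unit of randomisation, 1:1 within pairs; 32% of Veterans were hospitalized in 2007 (0.30 used below); matched CLCs have at least 50 beds.

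**Assumed, because not given.** Two-sided 5%; facility intraclass correlation (ICC) 0.03; facility-by-period ICC 0.01 (0 to 0.02 in sensitivity runs); 200 residents per facility-period (60 to 300 in sensitivity runs); coefficient of variation (CV) of facility size 0, 0.6 or 1.0; within-pair correlation of changes 0 to 0.6.

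**1. Equal sizes, no pair term, independent pair members (exact).** The uncorrected cluster variance equals the pooled variance times (G-2)/G. At G = 16 that is 14/16, so the variance is 12.5% too small. Two-sided error is:

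- Uncorrected, normal reference: 2·P(t14 > 1.96·√(14/16)) = 2·P(t14 > 1.833) = 8.8%.
- G/(G-1) factor, normal reference: 2·P(t14 > 1.96·√(14/15)) = 7.9%.
- G/(G-1) factor, t(15): 2·P(t14 > 2.131·√(14/15)) = 5.9%.
- Bias-corrected variance with t(14): 5.0%.

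At G = 30 the first three become 6.9%, 6.4% and 5.4%.

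**2. Unequal sizes (simulation).** Resident-level binary before/after difference-in-difference with no true effect, 8 pairs, independent pair members, 15,000 runs:

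| Method | CV 0 | CV 0.6 | CV 1.0 |
|---|---|---|---|
| Uncorrected, normal | 8.7% | 11.0% | 15.2% |
| G/(G-1), normal | 7.8% | 10.0% | 14.0% |
| G/(G-1), t(15) | 5.8% | 7.7% | 11.3% |
| Pair-level t, 7 df | 4.8% | 4.8% | 4.9% |
| Sign-flip over pairs | 4.3% | 4.5% | 4.7% |

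The simulated 8.7% at CV 0 agrees with the exact 8.8%. With 15 pairs the uncorrected version gives about 7-10%.

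**3. Correlated changes within pairs, still no pair term.** For the uncorrected version with a normal reference, at CV 0 / 0.6 / 1.0:

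- Correlation 0.3: 6.1% / 7.9% / 11.5%.
- Correlation 0.6: 3.5% / 4.1% / 7.8%.

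With the G/(G-1) factor and t(15), correlation 0.3 gives 3.8% / 5.4% / 8.1%.

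**4. Pair effects in the model, clustering left at the facility.** Let d_j be the within-pair difference in change for pair j, d̄ its mean and J the number of pairs. With equal sizes each facility's residual is ±(d_j - d̄)/2. The facility-clustered variance is then Σ(d_j - d̄)²/(2J²), against the correct Σ(d_j - d̄)²/{J(J-1)}. The ratio is (J-1)/(2J) = 7/16 at 8 pairs. Error is 2·P(t7 > 1.96·√(7/16)) = 2·P(t7 > 1.296) = 23.6%. With the G/(G-1) factor and t(15) it is 2·P(t7 > 2.131·√(7/15)) = 18.9%. The simulation gives 23.9% / 26.8% / 32.3% uncorrected and 19.2% / 22.2% / 27.5% with t(15); over all settings run the range is 18-33%.

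**5. The pair-level tests.** Over all the 16-facility settings the pair-level t test stayed at 4.3-5.3% and the sign-flip test at 3.7-5.2%. The smallest attainable two-sided sign-flip p with 8 pairs is 2/2⁸ = 0.0078.

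**The case against.** The plan says only that standard errors are clustered by facility. A bias-corrected variance with small-sample degrees of freedom also fits that description and restores 5% when sizes are equal. Even the common G/(G-1) factor with t(15) leaves only about 6% in that case. So one cannot say that the reported errors will be wrong, only that the plan does not prevent it. That stands. It does not remove the point: the plan commits to no correction, and the common one still gives 8-11% when sizes are unequal.

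Three stronger readings are tempting, and the documents do not support them.

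- **That the results must be too optimistic.** The direction depends on the within-pair correlation of changes, which is not reported. CLCs were matched on five years of monthly rates, so some correlation is plausible, and at 0.6 the test without a pair term is mostly conservative. On the other hand, differencing before and after already removes similarity in level, so a strong correlation of changes cannot be presumed.
- **That the analysis ignores the pairs.** The sentence on clustering follows one that calls the approach similar to the paired primary analysis. Whether pairs enter the resident-level model is simply not stated. If they enter as effects with clustering left at the facility, the inflation is larger, not smaller.
- **That the primary or safety results are affected.** The primary outcome is a facility-level rate compared within pairs. For mortality and ADL decline, Aim #4 states no clustering method, so nothing follows for them from this sentence.

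**Conclusion.** The point holds, within limits. In its usual form the stated method does not hold 5% at the planned minimum of 8 pairs. With no pair term and independent pair members, two-sided error is about 8-9% (equal sizes) and 10-15% (unequal) with a normal reference, or about 6% and 8-11% with the usual factor and t(15). It turns mostly conservative at a within-pair correlation near 0.6, and reaches 18-33% if pair effects are combined with facility clustering. The equal-size figures without correlation are exact. The others rest on assumed variance components, size spread and correlation. That one sentence of the plan is compatible with error rates from about 3.5% to 33% is the reason to settle the method in advance. The consequence is confined to the alternate resident-level outcomes.

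**What to change.** Make the randomised pair the unit of inference for the resident-level outcomes. For short and long stay separately, compute each CLC's risk-adjusted before/after change, take the difference within each pair, and test the mean difference with t on J-1 df or with an exact sign-flip test over pairs. If the resident-level model is kept, use a bias-reduced cluster variance with small-sample degrees of freedom, clustered at the pair, and report the pair-level test beside it. State alpha and sidedness for these analyses. Say separately which method applies to mortality and ADL decline.

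The cost is a few lines of code and no new data. For the same standard error, intervals widen by about 21% with 8 pairs (2.365/1.960 = 1.21) and about 9% with 15 pairs (2.145/1.960 = 1.09).
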